9.4.5 Pulse Oximetry (Part D)

For the treatment-emergent pulse oximetry measurements, a summary of observed values and change from baseline values will be provided at each visit by treatment group, for the percent of oxygen saturation.

9.4.6 Physical Examination

Physical examination (PE) results will be presented in individual subject data listings only. Clinically relevant changes identified after screening will be reported as AEs.

9.6 Pharmacodynamic Analysis (Part D Only)

The sweat chloride value for a given visit will be calculated as the mean of the non-missing sweat chloride measurements obtained on the left and right arms at that visit. If one of the two arm measurements at a time point is missing, the other will be used as the mean. A volume ≥ 15 μL is required for an accurate determination of sweat chloride. Any results reported as having volume < 15 μL will be considered missing. Any sweat chloride values reported as < 10 mmol/L or > 160 mmol/L will be considered missing.

The analysis of sweat chloride data will be based on the FAS. A summary of raw values and change from baseline values will be provided at each scheduled visit by treatment group and overall using descriptive statistics.

The same MMRM model as for ppFEV₁ will be used to analyze the change from baseline for sweat chloride. Adjusted means and 2-sided 95% CIs of the treatment effect through Day 29 (averaged over Day 15 and 29), with 2-sided *P* values for all within-group comparisons, will be estimated using MMRM.

In addition, a listing containing individual subject data at scheduled and unscheduled visits will be provided.

10 INTERIM AND IDMC ANALYSES

10.1 Interim Analysis

An IA of the continuous ECG data may be performed after all subjects in Part B have completed the Safety Follow-up Visit. These results will be reviewed by a small unblinded Vertex team.

10.2 IDMC Analysis

Not applicable

11 REFERENCES

Not applicable.

12 APPENDICES

Appendix A: Analysis Visit Windows (Part D Only)

Table 12-1 Analysis Visit Windows for Safety and Efficacy Assessments

Assessment	Visit ¹	Target Study Day	Analysis Visit Window ^{2,3,4} (in study days)
Safety Assessment			
Serum Chemistry	Baseline	1	≤1 Pre-dose
Hematology	Day 8	8	(1 ⁵ , 12]
Coagulation	Day 15	15	(12, 22]
Vital Signs (including Weight and BMI)	Day 29	29	(22, 43]
	Safety Follow-up	Not applicable	Use nominal visit
Standard 12-lead ECG	Baseline	1	≤1 Pre-dose
	Day 1 Postdose	Not applicable	Use nominal visit
	Day 8	8	(1, 12]
	Day 15 Predose and Postdose	Not applicable	Use nominal visit
	Day 29		(22, 43]
	Safety Follow-up	29	Use nominal visit
		Not applicable	
Efficacy Assessment and Pharmacodynamic Assessment			
Spirometry	Baseline	1	≤1 Pre-dose
Sweat Chloride	Day 8	8	(1, 12]
	Day 15	15	(12, 22]
	Day 29	29	(22, 43]
	Safety Follow-up	Not applicable	>43

Table 12-1 Analysis Visit Windows for Safety and Efficacy Assessments

Assessment	Visit ¹	Target Study Day	Analysis Visit Window ^{2,3, 4} (in study days)
Notes:			
Visit name for analysis purpose is used to report data in tables and figures.			
2 The analysis visit windows will be applied using the following rules for both scheduled and unscheduled visits: 
 If no numerical measurement is available within a visit window, the measurement will be considered missing for the visit. If there is more than 1 numerical measurement available within a visit window, use the following rules: 
 The measurement closest to the target day will be used; or If there are multiple measurements with the same distance from the target day, the latest measurement will be used. 			
3 For lab, ECG and vital sign measurement collected on the date of first dose of study drug in Treatment Period, if it cannot be determined whether the measurement is before or after the first dose: 
 Scheduled measurement will be treated as pre-dose observation. Unscheduled measurement will be treated as post-dose observation. 			
4 For safety assessment, Safety Follow-up analysis visit will be based on nominal Safety Follow-up visit. If a subject doesn't have a nominal Safety Follow-up visit but has an ETT visit with study day >43, then the ETT visit will be mapped into Safety Follow-up analysis visit.			
Derived Variables:			
1. Age (in years) at first dose date and nominal visit (for demographics, listing and the calculation of [percent] predicted spirometry variables): 
Obtain the age at informed consent (in days) in “yy, mm” format (e.g., 24 years, 6 months) from the Vital Signs (VS) page at the Screening Visit, and add 0.5 month to convert to days.
 
Obtain the informed consent date.
 
Then age (in years) at first dose or nominal visit = [(first dose date or nominal visit date – informed consent date) in days + age at informed consent (in days)]/365.25.
			
2. Missing first dose date or last dose date 
If the first dose date is missing, use Day 1 visit date to impute.
 
If the last dose date is missing or partial date is reported, the last dose date will be imputed based on, in descending order priority, the Early Treatment Termination (ETT) visit date, last visit date before the Safety Follow-up or the last study drug administration date from EX SDTM domain, as appropriate.
			
3. Sweat Chloride: 
Non-missing sweat chloride concentrations from the left arm and right arm with assessment end date/time for a given arm up to 30 minutes after first dose time in treatment period will be considered for baseline.
			
4. Electrocardiogram: 
Baseline is defined as the most recent pretreatment measurement before the first dose of study drug in the Treatment Period (or the average of triplicate measurements, if the most recent non-missing measurement is obtained in triplicate). If multiple ECG measurements are obtained on the same calendar day during the TE period, 
 ○ For summary purpose, the calculated average ECG will be used as the ECG value on that day (except for Day 1 and Day 15 for ECG in Part D); ○ For threshold analysis purpose, all reported ECG values will be used. 
			

Table 12-1 Analysis Visit Windows for Safety and Efficacy Assessments

Assessment	Visit ¹	Target Study Day	Analysis Visit Window ^{2,3, 4} (in study days)
5. Day 1 post dose could be included in the Analysis Visit Window.			

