i Standard 12-lead ECGs will be performed in the supine position after the subject has been at rest for at least 5 minutes. The ECG will be done before any other procedures that may affect heart rate, such as blood draws. On Days 1 and 15, ECGs will be collected before dosing and 4 hours (± 1 hour) after dosing. ECGs collected on Day 1 before dosing will be performed in triplicate.

j The predose assessment on Day 1 may be performed on the previous day (Day -1) if randomization has occurred.

k Sweat chloride will be measured in all subjects. See [Section 8.2.1](#) for information about the sweat chloride assessment for study eligibility.

l Spirometry may be performed pre- or post-bronchodilator at the Screening Visit. Spirometry will be performed pre-bronchodilator, before the morning dose of study drugs, and should be performed at approximately the same time at every other study visit. On Days 1 and 15, spirometry will also be performed pre-bronchodilator 5 hours (± 1 hour) after study drug administration.

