## Spirometry

Mild post-dose declines in lung function have been observed after the initial dose with another CFTR corrector not included in the current study (LUM). Although nonclinical toxicity results do not indicate a risk of lung function declines for VX-121, lung function, as assessed by spirometry, will be included in Part D to assess for post-dose declines in spirometric indices. In addition, lung function, as assessed by spirometry, will be evaluated for preliminary evidence of efficacy.

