### **11.7.5 Spirometry (Part D Only)**

Spirometry will be performed according to the American Thoracic Society Guidelines/European Respiratory Society Guidelines.

Spirometry will be performed as outlined below:

Pre-bronchodilator spirometry is defined as spirometry testing performed for subjects who have

- withheld their short-acting bronchodilators (e.g., albuterol) or anticholinergic (e.g., ipratropium bromide [Atrovent®]) for more than 4 hours before the spirometry assessment;
- withheld their long-acting bronchodilator (e.g., salmeterol) for more than 12 hours before the spirometry assessment; and
- withheld their once-daily, long-acting bronchodilator (e.g., tiotropium bromide [Spiriva®]) for more than 24 hours before the spirometry assessment.

During the Screening Period, spirometry assessments may be performed pre- or post-bronchodilator. At all other visits, all spirometry assessments should be performed “pre-bronchodilator.” During the Treatment Period, spirometry assessments must be performed before the morning dose of study drugs at approximately the same time at each visit. Postdose spirometry assessments will be performed as noted in [Table 3-7](#).

In the event that a subject forgets to withhold bronchodilator(s), spirometry should be performed according to the following:

- If a subject’s Day 1 Visit spirometry assessment is pre-bronchodilator but, on a subsequent visit, the subject forgets to withhold bronchodilator use, a post-bronchodilator spirometry assessment will be obtained for that visit only, and the visit will not be rescheduled.
- If, on the Day 1 Visit, the subject forgets to withhold his/her dose of bronchodilator, spirometry should be performed post-bronchodilator, and all subsequent spirometric measurements (according to the schedule of assessments detailed in [Table 3-7](#)) should be performed post-bronchodilator.
- Each spirometry assessment will be recorded in the source documents as pre- or post-bronchodilator.

If more than 1 spirometry assessment is required at a visit, bronchodilators will be withheld until completion of the last scheduled spirometry assessment.

All sites will be provided with spiroometers to be used for all study assessments. Spirometry data will be transmitted to a centralized spirometry service for quality review.

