9.3 Efficacy Analysis

9.3.1 Spirometry (Part D Only)

The spirometry parameters: FEV₁ (L), forced vital capacity (FVC) (L), FEV₁/FVC (ratio), and forced expiratory flow, midexpiratory phase (FEF_{25%-75%}) (L/s) and their corresponding percent predicted values (percentage point) and change from baseline will be summarized by treatment group using descriptive statistics for the FAS. Percent predicted FEV₁ is the ratio of FEV₁ (L) and predicted FEV₁ (L), expressed as a percentage. See [Appendix B](#) for more details.

In addition, a mixed-effects model for repeated measures (MMRM) with change from baseline at Day 15 and Week 4 predose for percent predicted forced expiratory volume in 1 second (ppFEV₁) as the dependent variable will be performed for the FAS. The model will include treatment group, visit, and treatment-by-visit interaction as fixed effects. The model will be estimated using restricted maximum likelihood. Denominator degrees of freedom for the *F* test for fixed effects will be estimated using the Kenward-Roger approximation. A compound symmetry covariance structure will be used to model the within-subject errors. Conditional on the fixed effects, missing data due to treatment or study discontinuation will be assumed to be missing at random.

The adjusted means and 2-sided 95% CIs of the treatment effect through Day 29 (averaged over Day 15 and 29), with corresponding *P* values for all within-group comparisons, will be estimated using MMRM.

In addition, the adjusted mean and 95% CI of the within-treatment difference at each post-baseline visit through Day 29 for each treatment group will be provided along with the *p*-value.

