9.4 Safety Analysis

Safety is the primary objective of this study. The overall safety profile of VX-121 will be assessed in terms of the following primary (safety) endpoints:

- Incidence of treatment-emergent adverse events (TEAEs)
- Clinical laboratory values as specified in the CSP.
- ECG outcomes
- Vital signs (including pulse oximetry [Part D only])
- Spirometry (Part D only)

All safety analyses will be performed by treatment group/treatment sequence for each part as applicable based on the Safety Set. All safety data will be presented in the individual subject data

listings based on the All Subjects Set. No statistical hypothesis testing will be performed for safety analysis.

Table 9-1 shows the safety summaries (e.g., raw value, change from baseline, incidence, and clinical abnormalities and etc) that will be summarized for TEAEs, clinical lab values, 12-lead ECGs, vital signs, spirometry and physical examination. Details are provided in the corresponding subsections.

The incidence of TEAEs will be summarized. TEAE summaries will include the following: all TEAEs (regardless of severity or relationship to study drug), serious adverse events (SAEs), TEAE severity, TEAE relationship, and discontinuations of study drug treatment due to TEAEs.

For the non-AE safety evaluations (clinical laboratory, ECGs and vital signs), raw values, and changes from baseline will be summarized as indicated in **Table 9-1**. For example, an “X” under the raw value column (third column) means that the “Raw value” for the safety evaluation will be summarized in tables; an “X” under the “Change from Baseline” column (fourth column) means that change will be summarized in tables.

Throughout this section, “change” refers to absolute change from baseline.

Table 9-1 Summaries Planned for Safety Data

Safety Assessment	Incidence	Raw Value	Change from Baseline	Clinical Abnormalities	Threshold Analysis
TEAEs	X			NA	
Hematology/and chemistry		X	X	Listing only	X (Part D only)
Coagulation		X (Part D only)	X (Part D only)		
Urinalysis		Listing only			
12-lead ECG		X	X		X (Part D only)
Vital signs		X	X		X (Part D only)
Spirometry (Part D)		X	X	NA	
Physical Examination		Listing only		NA	

ECG: electrocardiogram; TEAEs: treatment-emergent adverse events; NA: Not applicable; X: safety assessment will be summarized in tables

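### Part D spirometry windows place the 5-hour post-dose test in the Day 15 summaries and leave the Day 1 post-dose test in no analysis visit

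*SAP*

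**What the plan says.** **Schedule.** Protocol Table 3-7, footnote l, adds a second test on two days: "On Days 1 and 15, spirometry will also be performed pre-bronchodilator 5 hours (± 1 hour) after study drug administration". Protocol 9.3.3 explains why lung function is measured: it "will be included in Part D to assess for post-dose declines in spirometric indices", and also gives preliminary evidence of efficacy. Protocol 11.7.5 requires that treatment-period "spirometry assessments must be performed before the morning dose of study drugs at approximately the same time at each visit", with the post-dose tests as extras. Spirometry is a component of the Part D primary safety endpoint.

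**Windows.** SAP 9.1 sends all Part D protocol-defined visits to Appendix A. Table 12-1 there gives spirometry Baseline (study day 1 or earlier, pre-dose), Day 8 (1, 12], Day 15 (12, 22], Day 29 (22, 43] and Safety Follow-up (after day 43). Windows are in study days. Note 2 takes the value closest to the target day and then says: "If there are multiple measurements with the same distance from the target day, the latest measurement will be used".

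**ECG, for comparison.** In the same table ECG has a nominal Day 1 post-dose visit and a nominal "Day 15 Predose and Postdose" entry. The same-day averaging rule for ECG also carries an exemption, "except for Day 1 and Day 15 for ECG in Part D".

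**Analyses.** SAP 9.3.1 defines the mixed-model outcome as "change from baseline at Day 15 and Week 4 predose for percent predicted forced expiratory volume in 1 second". It also plans descriptive summaries of FEV1, FVC, FEV1/FVC and FEF25%-75% with no pre-dose qualifier. SAP 9.4 introduces Table 9-1 as showing the safety summaries "that will be summarized for TEAEs, clinical lab values, 12-lead ECGs, vital signs, spirometry and physical examination". For spirometry that table marks raw value and change from baseline.

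**The concern.** ECG and spirometry are both measured before and after dosing on Days 1 and 15, yet only ECG has analysis visits that keep the time points apart. For spirometry, a general tie-break written for repeat measurements decides which of two deliberately different tests represents Day 15, and it picks the later one. This looks like an omission rather than a choice.

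Two things are at stake. First, the Day 15 summary would hold a 5-hour post-dose value between pre-dose values at Baseline, Day 8 and Day 29, although the protocol asks for tests at about the same time of day. The planned comparisons are within-group, so a time-of-day shift common to both arms would not cancel. Second, no visible summary table shows the post-dose change that the extra tests were added to detect, although spirometry is part of the primary safety endpoint.

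**Working it through.** The plan states no figure to reproduce on this point, and no sample size or power calculation is involved. The check applies Table 12-1 and note 2 literally to the schedule.

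**Step 1. Map each scheduled session.**

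| Session | Window | Result |
|---|---|---|
| Day 1 pre-dose | Baseline | used |
| Day 1, +5 h | not pre-dose; (1, 12] excludes day 1 | no analysis visit |
| Day 8 pre-dose | (1, 12] | used |
| Day 15 pre-dose | (12, 22] | ties with +5 h, displaced |
| Day 15, +5 h | (12, 22] | same study day, later, selected |
| Day 29 pre-dose | (22, 43] | used |

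Days 8, 15 and 29 each carry a ±1 day visit window, giving 3 × 3 × 3 = 27 combinations of visit days. In 27 of 27 the Day 15 value selected is the post-dose one, and in 27 of 27 the Day 1 post-dose value has no visit.

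**Step 2. Can footnote 5 rescue Day 1 post-dose?** It says Day 1 post-dose values could be included, but as transcribed its marker is on the laboratory and vital-signs window only. Even if it applied to spirometry, a Day 1 value lies 8 − 1 = 7 days from the Day 8 target. An on-schedule Day 8 test lies at most 1 day away and would win.

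**Step 3. Would clock time change the tie?** Suppose distance were measured from the Day 15 dosing time, with the pre-dose test about 0.02 day before dosing and the other 5/24 = 0.21 day after. A visit on Day 15 gives 0.02 against 0.21, and one on Day 16 gives 0.98 against 1.21, so pre-dose wins both. A visit on Day 14 gives 1.02 against 0.79, so post-dose wins. The SAP does not describe this method, and it would mix time points between subjects.

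**Step 4. Count by-visit summary cells.** Each subject has 6 scheduled treatment-period sessions and 4 cells (Baseline, Day 8, Day 15, Day 29). With 12 subjects:

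- sessions: 12 × 6 = 72
- cells: 12 × 4 = 48
- sessions with no cell: 72 − 48 = 24, and 24/72 = 33%

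The 24 are 12 Day 1 post-dose tests (12/72 = 17%) and 12 Day 15 pre-dose tests (17%). The remaining 12 post-dose tests would be summarised under the plain label Day 15.

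**Step 5. Effect on the mixed model, only if the windowed value were used.** Let d be the mean post-minus-pre difference in ppFEV1 at Day 15. The reported estimate averages Days 15 and 29 with equal weight, so the shift is (d + 0)/2 = d/2. The documents give neither the size nor the sign of d. For an assumed d from −4 to +4 points, the average moves by −2 to +2 points in each arm. A compound-symmetry model fitted by restricted maximum likelihood to simulated data for 9 and 3 subjects gave these same shifts, including with one subject on active treatment missing Day 29.

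**The case against.** The strongest reply is that the only modelled spirometry analysis is already protected. SAP 9.3.1 asks for pre-dose values, and a specific rule for a named analysis should prevail over a general selection rule. On that reading the post-dose value never enters the model, the d/2 shift does not arise, and the 12 Day 15 pre-dose tests are used in the model even though they lack a descriptive cell. This stands as far as the model goes. It does not cover the descriptive spirometry tables, which have no such qualifier, and it leaves the model and the Day 15 table using different measurements under one visit label.

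It can also be said that Table 12-1 lists spirometry under efficacy rather than safety, so the safety summaries may not follow note 2. But SAP 9.1 applies Appendix A to Part D visits generally, and no other rule for spirometry is visible.

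Three further limits are fair. Table 12-1 is disturbed in the available text, so a missing footnote marker is weak evidence on its own; Step 2 does not depend on it. One SAP contents entry between 9.4.6 and 9.6 is redacted and might describe a post-dose summary. Finally, Part D has about 12 subjects, safety is descriptive, and the listings show every pre/post pair, so no data are lost.

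**Conclusion.** The concern holds. As written, the windowing rule makes the 5-hour post-dose test the Day 15 value in the descriptive and safety summaries, and gives the Day 1 post-dose test no analysis visit. For the ppFEV1 model the SAP contradicts itself, because Appendix A selects post-dose and section 9.3.1 selects pre-dose; it is not established that the model would use the wrong value.

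In size, 24 of 72 sessions lack a by-visit summary cell on the literal reading. Of these, 12 (the Day 1 post-dose tests) lack one whether or not section 9.3.1 takes precedence. The d/2 shift is conditional on following the appendix in the model, and any numerical range for it is an assumption. The conclusion assumes that distance is counted in whole study days, as the table states. The finding that no post-dose summary is planned covers visible text only. This should be fixed before database lock.

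**What to change.** In Table 12-1, add nominal spirometry rows for Day 1 post-dose, Day 15 pre-dose and Day 15 post-dose, as ECG has, and apply the note 2 tie-break within each time point. State that only pre-dose values feed the Baseline, Day 8, Day 15 and Day 29 efficacy summaries and the mixed model; this reconciles Appendix A with section 9.3.1.

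Preferably, also add one Safety Set table by treatment group showing same-day post-dose minus pre-dose change on Days 1 and 15. Neither document commits to that table, but it answers the question for which the protocol gives the post-dose tests.

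The cost is a few lines of SAP text and one small table. No new data are needed.

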#### **9.1.2.4 Early Termination of Treatment**

If the subject prematurely discontinues study drug, an Early Termination of Treatment (ETT) Visit should be scheduled as soon as possible after the subject decides to terminate study drug. Subjects who prematurely discontinue study drug will also be required to complete the Safety Follow-up Visit, approximately 28 days after their last dose of study drug. The assessments performed at the Safety Follow-up Visit are listed in [Table 3-7](#).

Subjects who discontinue from study drug dosing for any reason (except withdrawal of consent) will have a final PK blood sample drawn as soon as possible after the decision to discontinue study drug is made. Additional safety assessments may also be performed at the discretion of the investigator, including possible consultation with a specialist consultant. The Vertex medical monitor will be informed about these additional assessments, and any additional data collected (e.g., as the result of an outside consultation) will be considered part of the study record to provide the most complete safety profile of the study drug.

If the ETT Visit occurs 3 weeks or later following the last dose of study drug, then the ETT Visit will replace the Safety Follow-up Visit, and a separate Safety Follow-up Visit will not be required.

If the subject withdraws consent for the study, no further evaluations should be performed, and no additional data should be collected. Vertex may retain and continue to use any data and samples collected before such withdrawal of consent.

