9.2.5 Study Drug Exposure and Compliance

Study drug exposure in Parts B, C and D (i.e., duration of treatment) will be summarized by treatment group and overall for the Safety Set.

Study drug exposure (in days) will be defined as (last date of dosing – first date of dosing) + 1.

The study drug administration will be presented in an individual subject listing.

Compliance analysis will be provided for Part D only based on the FAS, and will be presented by treatment group and overall. Study drug compliance will be calculated as: $100 \times [1 - (\text{total number of days of study drug interruption}) / (\text{duration of study drug exposure in days})]$. A study drug interruption on a given day is defined as an interruption of any study drugs on that day. Study drug compliance will be summarized descriptively by the number of subjects (n), mean, SD, median, min, and max. It will also be summarized in categories: <80% and $\geq 80\%$ using frequency tables.

In addition, percentage of tablets taken will be calculated using the following formula: $100 \times [(\text{total number of tablets dispensed for the Treatment Period}) - (\text{total number of tablets returned})] / (\text{total number of tablets planned to be taken per day} \times \text{duration of study drug exposure in days})$. Summary similar to the study drug compliance will be produced based on the FAS for Part D only.

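### For a Part D subject with a missing or partial last dose date and a delayed ETT visit, the SAP's imputation order can overstate exposure by the full delay and distort compliance

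*SAP*

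**What the plan says.** SAP Appendix A, Derived Variables item 2, sets the trigger and the order: "If the last dose date is missing or partial date is reported, the last dose date will be imputed based on, in descending order priority", followed by "the Early Treatment Termination (ETT) visit date, last visit date before the Safety Follow-up or the last study drug administration date". The third source carries a qualifier: "the last study drug administration date from EX SDTM domain, as appropriate". No criterion for that qualifier is given. The rule sets no latest permissible date and does not require the result to agree with the known month or year of a partial date.

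Protocol 9.1.2.4 says that the ETT "Visit should be scheduled as soon as possible after the subject decides to terminate study drug". It also provides for delay, under the condition "If the ETT Visit occurs 3 weeks or later following the last dose of study drug"; a late visit of this kind stands in for Safety Follow-up.

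SAP 9.2.5 uses the date as follows: "Study drug exposure (in days) will be defined as (last date of dosing – first date of dosing) + 1". That duration is the denominator of both Part D compliance measures, the interruption-based one and the percentage of tablets taken. Each is also summarized as below 80% versus 80% or more.

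**The concern.** An ETT visit date is not a dosing date. It can equal the last dose date at best, and otherwise falls after it. Ranking it first means that, for a subject with an ETT visit, the dosing record is never reached unless someone invokes the undefined closing qualifier.

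The SAP also treats one visit in two ways. Table 12-1 note 4 maps an ETT visit after Day 43 to Safety Follow-up when there is no nominal follow-up visit, yet item 2 makes no exception for it. The same visit could serve as off-treatment follow-up and as the last day of dosing, giving at least 44 days of exposure in a treatment period planned to end at the Day 29 Visit.

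The subjects concerned are those who stop early. Their short exposure is what a reader of a tolerability study looks for, and with about 12 subjects one wrong value shows in an arm mean.

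**Working it through.** The documents give no expected exposure or compliance figure, so there is none to reproduce. The check applies the SAP 9.2.5 formulas to a hypothetical subject.

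**Inputs from the documents**
- Imputation order: SAP Appendix A, item 2.
- ETT possibly 21 or more days after last dose: Protocol 9.1.2.4.
- Last planned dose on the morning of the Day 29 Visit (± 1 day): Protocol Table 3-7.
- 9 active and 3 placebo subjects: Protocol Figure 9-1.

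**Assumptions**
- First dose on Day 1, true last dose on Day L, ETT visit g days later, and i interruption days before L.
- Days between last dose and ETT are not counted as interruption.
- All unused tablets are returned and counted.
- L and g are illustrative.

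**Formulas (true versus imputed from ETT)**
- Exposure: L versus L + g.
- Interruption-based compliance: 100 × (1 − i/L) versus 100 × (1 − i/(L + g)).
- Percentage of tablets: 100 × (L − i)/L versus 100 × (L − i)/(L + g). The number of tablets per day cancels.

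**Imputed exposure and percentage of tablets, i = 0** (true values: L days and 100%)

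| Last dose | g = 1 | g = 3 | g = 7 | g = 21 |
|---|---|---|---|---|
| Day 8 | 9 d, 88.9% | 11 d, 72.7% | 15 d, 53.3% | 29 d, 27.6% |
| Day 15 | 16 d, 93.8% | 18 d, 83.3% | 22 d, 68.2% | 36 d, 41.7% |
| Day 22 | 23 d, 95.7% | 25 d, 88.0% | 29 d, 75.9% | 43 d, 51.2% |

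For example, 8/(8 + 21) = 27.6%. A fully compliant subject drops below 80% when L/(L + g) < 0.8, that is g > L/4: more than 2 days at L = 8, 3.75 at L = 15 and 5.5 at L = 22. Interruption-based compliance stays at 100% throughout the table.

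**With interruptions.** For L = 8, i = 2 and g = 21:
- Interruption-based compliance goes from 1 − 2/8 = 75.0% to 1 − 2/29 = 93.1%, crossing the 80% line upward.
- Percentage of tablets goes from 6/8 = 75.0% to 6/29 = 20.7%.

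The two measures move in opposite directions.

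**Beyond the planned period.** With g = 21, any last dose on Day 10 or later gives an imputed date after Day 30 (10 + 21 = 31).

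**Arm means.** Suppose one subject stops on Day 8 with g = 21 and the others are dosed to Day 29.
- Active: (8 + 8 × 29)/9 = 26.7 days, reported as 29.0.
- Placebo: (8 + 2 × 29)/3 = 22.0 days, reported as 29.0.

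The early stop disappears from the mean.

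**TEAEs.** Under SAP 9.1 the last dose date sets the end of the Part D treatment-emergent period only when there is no Safety Follow-up Visit. With L = 8 and ETT on Day 29, that end moves from 8 + 28 = Day 36 to 29 + 28 = Day 57. Protocol 13.1.1.3 ends AE collection for such a subject at the earlier of Day 36 and the late ETT visit, so on Day 29. The longer window captures no further collected events.

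**MMRM.** The model and its visit windows do not use the last dose date.

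**The case against.** A reader might infer that Part D exposure and compliance are simply wrong for early stoppers. The documents do not support that, for four reasons.
- The rule acts only on a missing or partial date. A complete recorded date is never overridden.
- The ETT visit is meant to be prompt, and a delay of 3 weeks is the exception. With a 1-day gap at Day 15, exposure is 16 days instead of 15.
- The ETT visit includes a PK sample (Protocol Table 3-7). Protocol 11.3.1 and 9.6.2 call for a dosing record at PK visits, including the two preceding doses. If that record is made, the date should usually be known. Applying the 3-week provision also presupposes rough knowledge of the last dose.
- The closing qualifier leaves the analyst some room.

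All four stand as limits on frequency. None changes the value that the rule gives once triggered, and discretion without a criterion is not a prespecified rule.

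A reader might also infer that reversing the order cures the problem. It does not. Part D is outpatient, Protocol 9.6.2 specifies dose dates only around PK sampling, and the documents do not say how EX is populated. Suppose the true last dose is Day 27, the last EX date is Day 15 and a prompt ETT is on Day 28. The SAP order gives 28 days, 1 too many; a plain reversal gives 15, 12 too few. A drug-return date is no safe substitute either: subjects bring their drug back at visits, so it may be the ETT date itself. This objection stands and shapes the fix.

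**Conclusion.** The point holds in a narrow form and is minor. When a Part D last dose date is missing or partial and the ETT visit is delayed, item 2 overstates exposure by exactly the delay and lowers the percentage of tablets taken. It raises interruption-based compliance only if there were interruption days.

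The number of subjects affected is an assumption, because the documents give no rate: 0 or 1 of about 12. One subject is 11% of the active arm (1/9) or 33% of placebo (1/3).

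The effect is confined to descriptive exposure and compliance outputs. The longer fallback treatment-emergent window might suggest that the primary safety result is at risk, but AE collection has already ended, so TEAE counts do not change in practice. The MMRM results do not change.

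**What to change.** Replace the priority list in SAP Appendix A, item 2, before database lock with:
1. Use a complete last administration date from EX first, when drug accountability is consistent with its being the actual last dose.
2. Otherwise impute a date that keeps any known month and year and is no later than the earliest of the ETT visit date, the last visit before Safety Follow-up, and the actual or planned Day 29 Visit. State how the date within that limit is chosen.
3. Treat the ETT date only as an upper bound. Do not use as the last dose date an ETT visit that replaces Safety Follow-up, whether because it falls 3 or more weeks after the last dose or because Table 12-1 note 4 maps it there.
4. Put this criterion in place of the open-ended closing qualifier.

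The cost is a few sentences in the SAP and a small change to the derivation, with no new data. The downside is that where EX is incomplete the imputed date stays uncertain, so imputed cases should be flagged in the dosing listing.
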